9 CONTENT OF REPORTS

All analyses described in this SAP will be included in the Clinical Study Report(s) except where otherwise noted. Refer to the Data Presentation Plan for mock-ups of all tables and listings.

10 DOCUMENT HISTORY

Table 10-1: Document History

Version Number	Author(s)	Description
1.0		Initial Approval June 20, 2016
2.0		
Based on the protocol amendment 3, the following changes were made:
 
 1. Change the pre-study nivolumab requirement 2. Add a small increase to the sample size 3. Add immunogenicity as an endpoint 4. For the first interim analysis, replace 100 patients per arm with 25 patients per arm and add safety DMC every 6 months. 5. IMAE definition was updated and updated IMAE preferred term list was updated. 6. PFS rates at 6, 12 and 24 months by duration of prior nivo treatment (<3 months, ≥3-<6 months and ≥6 months; as well as OS rates at 6, 12, 18, 24, 36, 48 and 60 months. 7. Analysis of PFS and OS rate adjusting for stratification factors with inverse variance weight 8. Bootstrap analysis for OS for years 3, 4, and 5 9. For the first interim analysis, replace 100 patients per arm with 25 patients per arm. Add safety DMC every 6 months. 10. By duration of pre-randomization nivolumab treatment (i.e. <3 months, ≥3-<6 months and ≥ 6 months) is added for IMAE and serious AE. 11. Added per protocol population with details.
		Based on the protocol amendment 4, section 7.10 interim analyses were updated.
3.0		
Based on revised protocol 05, the following changes were made:
 
 1. Reduced sample size and modified primary endpoint from non-inferiority to one-sided confidence interval around the differences of PFS rates. 2. For sensitivity analysis of PFS rates at 6-month and 12-month, alpha adjustment will not be conducted. Instead, 95% one-sided confidence interval around the difference of PFS rates will be done. 3. Modified follow-up for overall survival for 3 years. For secondary endpoint, OS rates were updated up to 3 years. 4. Added rationale for maximum treatment duration with nivolumab of 2 year.

Table 10-1: Document History

Version Number	Author(s)	Description
		5. Update the dose delay definition. As per protocol schedule, +/- 2 days are allowed visit window.

[REDACTED]

APPENDIX 1 SELECT ADVERSE EVENTS DEFINITION AND CONVENTIONS

The select Adverse Events (select AEs) consist of a list of preferred terms grouped by specific category (e.g. pulmonary events, gastrointestinal events categories) and by subcategory (e.g. thyroid disorders, diabetes, pituitary, adrenal disorders subcategories). These categories and subcategories are defined by the Sponsor and the list that is most current at the time of analysis will be used. Also changes may be made to this list with each new version of MedDRA.

For information, the select AEs defined at the time of finalization of the first version of the document are listed in [Table 11-2](#) using MedDRA version 16. The updated list of select AEs will be used at the time of analysis and the final list used for the clinical study report will be included in an Appendix of the CSR.

Time-to onset definition

Time-to onset of select AE (any grade) for a specific category (i.e. pulmonary events, gastrointestinal events, ...) is defined as the time between the day of the first dose of study treatment and the onset date of the earliest select AE (of any grade) in this category.

If the subject did not experience a select AE (of any grade) in the category, time-to onset will be censored at the maximum follow-up time for all subjects in their respective treatment group (i.e. for subjects without an event, follow-up time is defined from first dosing date up to last dosing date + 30 days (or 100 days depending on the analysis), otherwise it is defined up to the last known alive date). The resulting Kaplan-Meier plot will present the cumulative rate of the select AE (any grade) in the category over time.

Time-to onset of select AE (grade 3-5) for a specific category is defined similarly but restricted to grade 3-5 select AEs.

Time-to onset of drug-related (grade 3-5 or any grade) select AE for a specific category is defined similarly but restricted to drug-related select AEs.

Time-to onset for a specific subcategory is defined similarly but restricted to event of this subcategory.

Time-to resolution definition

In order to derive the time-to resolution, overlapping or contiguous select AEs within a specific category (defined in [Table 11-2](#)) will be collapsed into what will be termed “clustered” select AEs. For example, if a subject (without pre-treatment AE) experienced an AE from 1st to 5th January, another AE (with different PT but within same category) from 6th to 11th January and same AE from 10th to 12th January, these will be collapsed into one clustered select AE from 1st to 12th January. [Table 11-1](#) is summarizing key derivation steps for each type of clustered select AEs.

Time-to resolution of select AE (any grade) for a specific category is defined as the longest time from onset to complete resolution or improvement to the grade at baseline among all clustered select AEs in this category experienced by the subject. Events which worsen into grade 5 events (death) or have a resolution date equal to the date of death will be considered unresolved. If a

clustered select AE is considered as unresolved, the resolution date will be censored to the last known date alive. Improvement to the grade at baseline implies that all different AE events in the clustered select adverse event should at least have improved to the corresponding (i.e. with same preferred term) baseline grade. This measure is defined only for subjects who experienced at least one select AE in the specific category.

The time-to resolution of select AE (grade 3-5) for a specific category is defined similarly with an onset date corresponding to a grade 3-5 select AE.

Time-to resolution of drug-related select AE (any grade or grade 3-5) is defined similarly but restricted to drug-related select AE.

The time-to resolution of select AE (any grade or grade 3-5, drug-related or all) where immune modulating medication is initiated is defined similarly with the additional condition that the subject started an immune modulating medication during the longest select AE resolution period.

Time-to resolution for a specific subcategory is defined similarly but restricted to event of this subcategory.

Table 11-1: Derivation of clustered select AE

Type of clustered select AE	Derivation
Any grade	Collapse any on-treatment select AE from the same category
Drug-related of any grade	Collapse any on-treatment drug-related select AE from the same category
Grade 3-5	Collapse any on-treatment select AE from the same category. Resolution will be based on the onset date of the earliest grade 3-5 records (if no grade 3-5 record, clustered select AE is excluded)
Drug-related of Grade 3-5	Collapse any on-treatment drug-related select AE from the same category Resolution will be based on the onset date of the earliest grade 3-5 record (if no Grade 3-5 record, clustered select AE is excluded)

The algorithm for collapsing select AE records is using the following conventions:

For each subject and specified category, the corresponding AE records will be collapsed when:

- 1) Multiple adverse event records have the same onset date.

- 2) The onset date of an event record is either the same day or 1 day later than the resolution date of a preceding event record (contiguous events).
- 3) The onset date of an event record is after the onset date and prior to or on the resolution date of a preceding event record (overlapping events).

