7.6.6.2 Time-to onset of IMAE

See Core Safety SAP.

Time-to onset of the following IMAE will be summarized for each category by treatment arm:

- Time-to onset of any grade IMAE where immune modulating medication was initiated
- Time-to onset of grade 3 to 5 IMAE where immune modulating medication was initiated
- Time-to onset of any grade Endocrine IMAE
- Time-to onset of grade 3 to 5 Endocrine IMAE

The median time-to onset and range summary statistics will be reported.

Additional details regarding the time-to onset definition and censoring rules are described in time-to onset definition subsection of [APPENDIX 1](#).

The analyses will be conducted using the 100-day safety window.

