7.10 Interim Analyses

The first safety interim analysis will be conducted after 25 subjects per treatment arm with at least 3 months of treatment exposure after randomization. It is anticipated that the DMC will meet at every 6 months to perform safety assessments.

In addition to the interim analyses specified above, additional interim analyses might be conducted, for example, to address regulatory questions or requests.

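### Read literally, the SAP's time-to-onset rule plots events/N under a Kaplan-Meier label: usable once all safety windows have closed, too low at any earlier data cut

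*SAP*

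**What the plan says.** The time-to onset definition in SAP Appendix 1 states that, for a subject without a select AE in the category, "time-to onset will be censored at the maximum follow-up time for all subjects in their respective treatment group". A bracket then explains follow-up. For subjects without an event, "follow-up time is defined from first dosing date up to last dosing date + 30 days", with 100 days as the alternative for some analyses; "otherwise it is defined up to the last known alive date". The appendix continues: "The resulting Kaplan-Meier plot will present the cumulative rate of the select AE (any grade) in the category over time".

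The rule reaches beyond select AEs. SAP 7.6.6.2 (IMAEs) says "Additional details regarding the time-to onset definition and censoring rules are described in time-to onset definition subsection of" Appendix 1, and SAP 7.6.7.2 (select AEs) and 7.6.8.2 (other events of special interest) refer to the same subsection. Select AE onset uses the 30-day window. For IMAEs, "The analyses will be conducted using the 100-day safety window", and the same holds for other events of special interest. All three sections also refer to a Core Safety SAP, which is not among the documents.

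Neither the protocol nor the SAP names cumulative incidence or competing risks as the target of these curves.

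**The concern.** A Kaplan-Meier curve should drop a subject from the risk set when that subject's observation for the event ends. Here events stop being counted 30 or 100 days after the last dose, yet an event-free subject stays in the risk set until the longest follow-up in the arm. Someone who stops at month 2 is carried as event-free for as long as the longest-followed subject. So is someone randomized shortly before a data cut, who has not yet had the chance to have the event.

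Elsewhere the SAP follows the usual practice. The treatment-duration curve in SAP 7.4.1 censors subjects still on therapy at their own last dose date, and SAP 7.6.10 reports exposure-adjusted AE rates. At stake is whether the displayed cumulative rates of immune-mediated and select AEs mean what their label says, and whether they are right at a cut made while treatment continues.

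**Working it through.** The documents give no AE onset rate or curve value, so there is no figure to reproduce. The check has four steps.

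**1. What the rule computes.** If no event-free subject leaves before the group maximum, the risk set at each onset time is N minus earlier events. The Kaplan-Meier product then telescopes to 1 − KM(t) = (events by t)/N.

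Example with ten subjects: events at 2, 6 and 8 months, four event-free exits at 4 months, the rest followed to 12, 24 and 24 months.
- Rule as written, at 12 months: 3/10 = 30%.
- Own-follow-up censoring: 1 − (9/10)(4/5)(3/4) = 46%.

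**2. When events/N is a legitimate quantity.** If every window has closed and nobody was lost, each subject's outcome within the window is known. Events/N is then the cumulative incidence with death or end of window as a competing event. Protocol 3.1 and 4.5 and SAP 2.1 cap treatment at 2 years, so windows close by 24 + 100/30.4375 = 27.3 months, inside the 3-year study. SAP 6.2 gives a 5-year maximum; these passages must be reconciled.

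**3. Distance from an own-follow-up Kaplan-Meier curve, closed form.** Assume a constant onset hazard λ. Let discontinuation follow the 12-month PFS of 0.48 in SAP 5, so μ = −ln(0.48)/12 = 0.0612 per month. Let w be the window in months (30/30.4375 = 0.986 or 100/30.4375 = 3.285). The rule shows at 12 months

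1 − e^(−λw) + e^(−λw) · λ/(λ+μ) · [1 − e^(−(λ+μ)(12−w))].

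- True on-drug risk 20%, λ = −ln(0.8)/12 = 0.0186. With w = 0.986: 0.018 + 0.982 × 0.233 × 0.585 = **15.2%**. With w = 3.285: 0.059 + 0.941 × 0.233 × 0.501 = **16.9%**.
- True on-drug risk 10%, λ = −ln(0.9)/12 = 0.0088: **7.5%** and **8.4%**.

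**4. Simulation (400,000 subjects).** Time on treatment follows both PFS rates in SAP 5: hazard −ln(0.63)/6 = 0.0770 per month to month 6, then −ln(0.48/0.63)/6 = 0.0453, capped at 24 months. Assumed onset hazards: 0.01; 0.03; or 0.05 for 3 months then 0.01 per month. Early cuts assume uniform accrual over 24 months. Entries are % at 12 / 24 months.

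| Window, onset hazard | Rule, windows closed (= cumulative incidence) | Own-follow-up KM | Rule, cut 6 months after last entry | Rule, cut 12 months after last entry |
|---|---|---|---|---|
| 30 d, 0.01 | 8.2 / 12.1 | 11.3 / 21.4 | 7.9 / 9.9 | 8.2 / 11.3 |
| 30 d, 0.03 | 22.2 / 30.5 | 30.3 / 51.3 | 21.3 / 25.8 | 22.2 / 28.7 |
| 30 d, 0.05 then 0.01 | 18.0 / 21.5 | 21.3 / 30.2 | 17.7 / 19.5 | 18.0 / 20.7 |
| 100 d, 0.01 | 9.2 / 13.5 | 11.3 / 21.3 | 8.8 / 11.0 | 9.2 / 12.5 |
| 100 d, 0.03 | 25.0 / 34.2 | 30.3 / 51.4 | 23.9 / 28.9 | 25.0 / 32.2 |
| 100 d, 0.05 then 0.01 | 19.5 / 23.3 | 21.3 / 30.3 | 19.1 / 21.1 | 19.5 / 22.5 |

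- Windows closed: the gap to cumulative incidence is 0. The gap to own-follow-up KM is 1.8-8.1 points at 12 months and 7.0-20.8 points at 24 months.
- Cut 6 months after last entry: below cumulative incidence by 0.3-1.1 points at 12 months and 2.0-5.3 points at 24 months.
- Cut 12 months after last entry: below by 0 and 0.8-2.0 points.

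**The case against.** **The final curve is a valid quantity.** A reader might infer that the cumulative rates are always understated. Step 2 shows otherwise: with all windows closed the curve is a correct on-treatment cumulative incidence, loss to follow-up aside. This stands, and the point is limited accordingly.

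**The Kaplan-Meier benchmark is a choice of estimand.** The assumed 20% is the risk if nobody stopped treatment, and no section sets that as the target. Own-follow-up censoring assumes non-informative discontinuation and gives more than the incidence actually seen. This also stands. The gap to that curve is an error only in so far as the plot is called Kaplan-Meier.

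**Larger figures are easy to produce.** Ending AE observation at the last dose in step 3 would give 14.4% and 7.1%, but that ignores the SAP's own 30- and 100-day windows. A cut with half an arm followed for only 6 months would show about 15% for a 20% risk (0.5 × 20% + 0.5 × 10.6%, where 10.6% = 1 − 0.8^0.5), but no section describes such a cut.

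**Few outputs are exposed.** The incidence tables do not use the rule. The onset sections ask for a median and range without saying that the median comes from a Kaplan-Meier estimate, as the resolution sections do. No section says that onset curves go to the DMC. All this stands. However, early cuts are provided for. SAP 2.5 plans a formal review, including safety data, at a minimum of 6 months after the last patient's first visit. One co-primary endpoint is at 12 months while treatment may run for 2 years. SAP 7.10 adds that "additional interim analyses might be conducted", and SAP 9 allows for more than one study report.

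**The bracket may mean own follow-up.** It opens by referring to subjects without an event, so a programmer could read it that way. But its last clause covers subjects with an event, who are never censored, so it has a purpose only as input to a group maximum. The literal reading is the more natural one, and two defensible readings are themselves a reason to rewrite the sentence.

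**Conclusion.** The concern holds in limited form. On its natural reading the rule yields events/N, which is not the Kaplan-Meier estimate it is called. That identity and the direction of the difference follow from the text alone.

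- **All windows closed:** mislabelled but usable as cumulative incidence. Against an own-follow-up Kaplan-Meier curve, a 20% 12-month risk shows as about 15% or 17%, and a 10% risk as about 7.5% or 8.4%.
- **Subjects still under observation:** low under either target. Against cumulative incidence the shortfall is about 0.3-1 point at 12 months and 2-5 points at 24 months for a cut 6 months after last entry, and 0 and about 1-2 points for a cut 12 months after last entry.

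The sizes rest on assumed onset hazards and accrual and on PFS as a proxy for time on treatment.

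A reader might also infer that the comparison between arms is biased. The documents do not support that: the rule is identical in both arms and would distort the contrast mainly if exposure or follow-up differed between them. The median onset is affected only if it is read from the Kaplan-Meier curve.

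**What to change.** Choose one target and rewrite the sentence in SAP Appendix 1, including its bracket.

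- **Keep the Kaplan-Meier label:** 'Subjects without the event are censored at the end of their own follow-up (last dose + 30 or 100 days, death, or data cut, whichever is first).'
- **Or declare cumulative incidence:** use the Aalen-Johansen estimator with death and end of the treatment window as competing events, censor only at the data cut or loss to follow-up, and relabel the plot.

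State also whether the median onset in SAP 7.6.6.2, 7.6.7.2 and 7.6.8.2 is taken among subjects with the event or from the curve, and check that the Core Safety SAP does not carry a different rule.

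The cost is a short SAP edit and reprogramming of one derivation, with no change to data collection. Under the first option, displayed late cumulative AE rates become somewhat higher and rest on non-informative discontinuation. Under the second, the curve is unchanged once all windows have closed, loss to follow-up aside, and is corrected at earlier cuts.
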